#### Interim and final analysis

Since the point estimators regarding proportion of measurements with a NRS  $\geq$ 4, used in our sample size calculation for non-inferiority, were based on a small pilot study they may have limited reliability. We therefore established a Data Safety Monitoring Board (DSMB), including a methodologist, statistician and two clinical experts (anaesthesiologist and thoracic surgeon) to assess whether our study generates sufficient power to answer the research question. When 50% of the observations in the TEA group (control) were completed (n=75), the DSMB performed an interim analysis to evaluate the point estimator and variance of the proportion of NRS measurements ≥4 of the control group and advised whether adjustment of our sample size was necessary. The DSMB only had access to all patients who underwent TEA and could warn the research team of potential risk factors and suspension of inclusions. The interim analysis by the DSMB was performed in January 2023. Based on pain scores of 70 complete TEA patients (4 patients had missing data and 1 patient was treated as TEA but randomized for ICNB) in the ITT analysis, no changes in the sample size were required. The final analysis will be performed when all data of 450 patients is collected. No specific stopping rules apply since the OPtriAL has been classified as having negligible risk for study subjects. The SPIRIT flow diagram in Table 1 of the published protocol (1) demonstrates a complete overview of the schedule of assessments.

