#### Baseline characteristics

Baseline characteristics will be described by trial arm as illustrated in Table 1 and assessed descriptively for the ITT group. In case of missing data, the denominator will not match with the total number of patients and this will be indicated in the corresponding table. Missing baseline characteristics will not be imputed.

Since stratification and randomization are applied to ensure a balanced distribution of baseline characteristics, we assume any differences to be caused by chance and to be a property of the sample, not of the population. Nevertheless, an imbalance of prognostic factors should not be ignored as it can influence the estimation of treatment effects. Therefore, all baseline characteristics in Table 1 will be compared between TEA versus PVB and TEA versus ICNB by using a validated method of standardized mean differences (SMDs) as described by Nguyen et al (9). The SMDs for these important prognostic variables will be reported in Table S1 (Supplemental material) and identified as potential imbalanced factors when the SMD exceeds 25%.

In Table 2, we will portray all details regarding the execution of the analgesic techniques including when it was performed (before, at the beginning, at the end or after the operation) and medication given (type, dosage and volume). For the TEA group we will report the test dose and continuous epidural mixture (local anaesthetics and opioids). The infusion rate (numerical in mL) from the time of placement until removal of the epidural catheter will be noted to calculate a total dosage (in milligram [mg] or microgram [ug]) of mixture given, reported as a continuous outcome. For the PVB group, the initial perioperative bolus given and the continuous infusion rate (in mL) until the day the PVB is stopped, will be recorded. For both TEA and PVB, also the number of days continuous infusion

was given will be noted. For the ICNB group the local anaesthetic given and the number of covered intercostal levels will be recorded. Any complication occurring during the execution of the analgesic technique will be reported in the text of the manuscript. Surgical and (general) anesthesia baseline characteristics will be shown in detail in Table 1.

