#### Analysis

For appointing non-inferiority, both the ITT and PP will be performed and both should attain to the predetermined non-inferiority margin (the one-sided 98.65% CI upper bound of the difference in proportions not exceeding 17.5%). For superiority (p<0.027), the ITT analysis will be considered as the primary analysis and the PP as a supportive analysis. For secondary outcome measures, solely the ITT analysis will be performed.

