#### Patient replacement and missing data

In the sample size calculation, we have considered 12.6% extra inclusions due to drop-outs after conversions to thoracotomy (late exclusion). Since this percentage is appropriately represented by data from the Dutch Clinical Audit database from 2017, we do not expect further patient

replacement. Clinical data management is performed by independent professional data managers from the Dutch Comprehensive Cancer Centre. Once inclusions are complete, careful inspection of the data will take place. The mechanism causing data to be missing, whether it is (completely) at random or not at random, will guide the study group to apply analytical methods to amend missing data.

The incidence of missing data is partially limited by study design where minimum numbers of measurements suffice to generate an outcome value. For our non-inferiority research question regarding pain, complete cases include patients with at least 3 NRS measurements during POD 0 until 2 or a LOS  $\leq$  2 days, to allow detection of curvilinear pain patterns over time for reliable imputation. The cut-off for LOS  $\leq$  2 days is established due to the expectation that patients who have been discharged from the hospital have a NRS score  $\leq$  4 (standard of care). For our superiority question regarding QoR, complete cases include patients with at least one QoR-score during POD 0 until 2.

In case of remaining patients with lacking outcome data below 5% of the study size (14), the baseline Table 1 will be reproduced for patients intended to be included in the analysis as complete cases and added to the supplementary material (15). Imbalances in covariate distributions across groups derived from observed SMDs in this table, will be assessed from a clinical perspective for potential bias in prognosis and adjusted for in a primary analysis based on complete cases.

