In case of remaining patients with lacking outcome data at or above 5% of the study size, the same procedure will be followed including a reproduced baseline table. In addition, missing data patterns will be studied to assess the likelihood of data being missing (completely) at random. If data are likely to be missing completely at random, multiple imputation (e.g. K-nearest neighbour imputation; multiple imputation by chained equation) and inverse probability weighting will be applied with presumably prognostic co-variates to substantiate the findings of the primary analysis. If data are likely to be missing at random, exploratory subgroup analyses will be run to restrict the target population for implementation of study results to the subgroups of patients closest to the observed

effect estimate in the complete case analysis. Restriction on the generalizability of study results will be fully reported in the supplementary material and discussed in the manuscript.

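### Intra-operative rows that the allocated technique may change are screened as chance baseline imbalance and can be adjusted for in a primary analysis of both co-primary outcomes

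*SAP*

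**What the plan says.** **Screening.** Under Baseline characteristics, "all baseline characteristics in Table 1 will be compared between TEA versus PVB and TEA versus ICNB" by SMD. Of arm differences the SAP says "we assume any differences to be caused by chance and to be a property of the sample, not of the population". Rows are "identified as potential imbalanced factors when the SMD exceeds 25" percent. The same section adds that "Surgical and (general) anesthesia baseline characteristics will be shown in detail in Table 1". Tables 1 and S1 accordingly list operating time, opioids and local anaesthetics under both induction and sustained analgesia, and vasopressives, next to age, sex and comorbidity.

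**Adjustment.** Under Patient replacement and missing data, when fewer than 5% of patients lack outcome data, Table 1 is reproduced for the complete cases. Imbalances in it "will be assessed from a clinical perspective for potential bias in prognosis and adjusted for in a primary analysis based on complete cases". At 5% or more, "the same procedure will be followed including a reproduced baseline table". Additional analyses adds a multiple regression of both co-primary outcomes for SMDs above 25%.

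**Decision rules elsewhere.** Analysis and Co-primary outcomes base non-inferiority on the confidence limit for the difference in mean proportions. For superiority, "the ITT analysis will be considered as the primary analysis and the PP as a supportive analysis". Appendix A lists a t-test or Mann-Whitney test for QoR-15. None of these mentions covariates.

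**The concern.** A covariate can be adjusted for safely in a randomised comparison when the treatment cannot have altered it. Several Table 1 rows do not clearly meet that condition. Table 2 records the epidural as placed pre-operatively with a perioperative infusion rate, the paravertebral block as given at the beginning of the operation, and the intercostal block as given at its end. The arms therefore differ in what regional analgesia is active during surgery. An arm difference in intra-operative opioid use may be a result of allocation rather than chance.

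If such a row enters the model, the contrast no longer estimates the total effect of the randomised technique. The sign of the shift depends on how the row relates to the outcome, so it cannot be called conservative in advance.

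A second problem is that the SAP describes two kinds of primary analysis, unadjusted and adjusted complete-case, and does not say which decides.

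**Working it through.** **1. Can the rule reach these rows?**

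- Screening covers the whole of Table 1, with no filter for timing.
- The only gate before adjustment in the missing-data section is a clinical judgement about prognosis. A variable that carries part of the treatment effect is itself prognostic, so this gate does not exclude it. The 25% threshold is not restated there.
- The regression under Additional analyses uses the 25% threshold and states no clinical gate, although its contrasts are reported only if thought opportune.
- The missing-data route opens once any patient lacks outcome data, because both branches use the same procedure. At the interim, "4 patients had missing data and 1 patient was treated as TEA but randomized for ICNB". That is 4/75 = 5.3% of epidural patients (exact 95% CI 1.5% to 13.1%). The SAP does not say whether those four would count as complete cases under its own rule.

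**2. Which rows does the screen pick?** Evaluable patients per arm: 150 × (1 − 0.126) = 131. The standard error of an SMD is about √(2/131) = 0.124.

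- A row unaffected by treatment exceeds 0.25 by chance with probability 2 × [1 − Φ(0.25/0.124)] = about 4.3%.
- A row shifted to 60% v 40% (assumed; SMD 0.41) exceeds it with probability of about 90%.

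A row that the technique shifts clearly is therefore far more likely to be flagged than a true baseline row.

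**3. The plan's own figure.** Pilot SDs are 19.57 and 23.33, and the pilot difference is 21.21 − 17.57 = 3.64.

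- Pooled SD = √[(19.57² + 23.33²)/2] = 21.53
- SE = 21.53 × √(2/131) = 2.66
- z(0.9865) = 2.2115
- Power = Φ[(17.5 − 3.64)/2.66 − 2.2115] = 99.9%, in line with the stated 99%
- Expected upper limit = 3.64 + 2.2115 × 2.66 = 9.52

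**4. Size of the shift.** Adjustment moves the contrast by the arm difference in the covariate times its within-arm slope, which equals SMD × r × SD of the outcome. SMD 0.25 to 0.5 and r 0.1 to 0.3 are assumptions. For a yes/no row, these SMDs correspond to 50% v 62% and 50% v 74%. The standard error is held fixed.

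| | SMD 0.25, r 0.1 | SMD 0.5, r 0.3 |
|---|---|---|
| Shift in SD units | 0.025 | 0.15 |
| Pain shift, percentage points (× 21.53) | 0.54 | 3.23 |
| Expected upper limit if the shift is adverse | 10.06 | 12.75 |
| Share of QoR-15 target effect | 0.025/0.432 = 5.8% | 0.15/0.432 = 34.8% |

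The QoR-15 target is the effect implied by 90% power at two-sided 0.027: (2.2115 + 1.2816) × √(2/131) = 0.432 SD. A simulation with a binary covariate and 131 per arm gave mean shifts of 0.025 and 0.150 SD, which confirms the formula.

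To reach the pain margin, SMD × r would have to be (17.5 − 9.52)/21.53 = 0.37.

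**5. If the true pain difference were at the margin.** A simulation set the true difference at 17.5, let the technique shift the covariate by 0.3 to 0.8 SD, and let the covariate carry 2 to 6 points of pain proportion per SD (all assumed). Adjustment lowered the contrast by about 0.6 to 4.8 points. False non-inferiority rose from the nominal 1.35% to between about 2% and 30%. With the opposite slope the bias runs the other way.

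**The case against.** The SAP nowhere says that an intra-operative row will be adjusted for. Clinical judgement comes first in the missing-data section, and the other regression is labelled additional. The explicit decision rules are unadjusted. Harm therefore needs a chain: missing outcome data, an imbalance in an affected row, a decision to adjust for it, and that result taking precedence. This stands, and it limits the severity.

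The SAP also never states that the technique changes these rows. The local anaesthetics row is unclear, since block drugs are recorded in Table 2. The firmest examples are the opioid rows, which are yes/no counts with no expected frequency given. This stands too, but the timing entries in Table 2 make an effect plausible, and the SAP's assumption of chance rules it out without argument.

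The bias sizes rest on assumed inputs, and the pilot difference concerns continuous locoregional analgesia, so it has no stated basis for the single-shot intercostal block. This is correct. The interim missingness covers epidural patients only and shows just that missing data occur.

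Last, a strict pre-randomisation rule also drops type of resection and port technique, which the analgesic technique is not argued to affect. That is a fair cost, but a small one if the adjusted analysis is only supportive.

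None of this answers the two core points: the adjustment set has no limit by timing, and the status of the adjusted analysis conflicts with the unadjusted rules.

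**Conclusion.** The concern holds and should be fixed; confidence is medium. Adjustment for a row affected by the technique is permitted, not required, and the unadjusted tests are untouched. The exposure lies in the adjusted complete-case analysis and, less so, in the additional regression.

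On the assumed ranges, the non-inferiority conclusion for pain is robust if the true difference is near the pilot value; it would not be if the true difference lay close to the margin. QoR superiority is the more exposed co-primary, since up to about a third of the target effect could be added or removed. These sizes depend on the assumed SMDs and correlations, on 131 evaluable patients per arm and, for pain, on the pilot SDs. The conflict over which primary analysis decides depends on none of them.

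**What to change.** - In Baseline characteristics, Patient replacement and missing data, and Additional analyses, limit SMD screening and covariate adjustment to variables fixed before randomisation.
- Report the intra-operative surgical and anaesthesia rows of Tables 1 and S1 descriptively, under their own label and without the assumption of chance.
- State in Patient replacement and missing data that the unadjusted analyses under Analysis and Co-primary outcomes decide non-inferiority and superiority, and that any adjusted complete-case analysis is supportive.
- Optionally, name the covariates of any adjusted analysis in advance: centre, and the pre-operative NRS or QoR-15 score, both of which are already collected. If the team wants to keep type of resection or port technique, it should name them now with the reason why the analgesic technique cannot affect them.

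The cost is SAP wording and table layout, with no new data. The change should be made before the final data are examined by arm.

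### Imputation and weighting are planned only if data look missing completely at random; under missing at random the SAP substitutes a circular subgroup restriction

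*SAP*

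**What the plan says.** The rule is in the SAP section Patient replacement and missing data. Below 5% of patients lacking outcome data, the baseline table is rebuilt for the complete cases. Imbalances seen in its standardised mean differences (SMDs) are "assessed from a clinical perspective for potential bias in prognosis" and "adjusted for in a primary analysis based on complete cases".

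At 5% or more, "the same procedure will be followed including a reproduced baseline table", and one further step depends on the presumed mechanism:

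- MCAR: "If data are likely to be missing completely at random, multiple imputation" is added, and "inverse probability weighting will be applied with presumably prognostic co-variates to substantiate the findings of the primary analysis".
- MAR: "If data are likely to be missing at random, exploratory subgroup analyses will be run to restrict the target population" for which the results are to be implemented "to the subgroups of patients closest to the observed" complete-case effect estimate.

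The same section mentions imputation once more. It gives the reason for requiring at least three pain scores as "to allow detection of curvilinear pain patterns over time for reliable imputation". That sentence defines who counts as a complete case. It names no method and does not cover patients who lack the outcome.

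**The concern.** The two branches are matched to the wrong mechanisms. Under MCAR the complete cases are a random subset, so their estimate is unbiased and imputation or weighting is least needed. Under MAR these two methods can correct a complete-case analysis, and there the plan names neither for the co-primary outcomes.

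What it adds under MAR cannot do their job. Subgroups are kept because they agree with the complete-case estimate, which is the very estimate in doubt. Agreement with it says nothing about its bias.

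At stake is mainly the quality-of-recovery (QoR) claim. The Summary of the study protocol justifies the wide pain margin partly by superiority on QoR, so a false or missed QoR result affects how the trial as a whole is read.

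The SAP is also at odds with itself. Its section on pain scores during rest and mobilisation accepts MAR as the working assumption of the linear mixed model, and the QoR-15 section plans the same type of model. Both are secondary analyses of the trend over time, with no stated contrast for the mean of postoperative days (POD) 1 and 2, so they do not fill the gap.

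**Working it through.** **Inputs from the SAP.** 450 patients, 150 per arm; 12.6% drop-out; one-sided alpha 0.0135 for pain and two-sided 0.027 for QoR; QoR power 90%; pilot pain proportions 17.57% (SD 19.57) and 21.21% (SD 23.33); margin 17.5 points (Summary of the study protocol). At the interim analysis 4 of 75 epidural (TEA) patients had missing data (Interim and final analysis).

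**The plan's own figures.** Evaluable per arm: 150 × 0.874 = 131. Pooled pilot SD: √((19.57² + 23.33²)/2) = 21.53. Gap between pilot difference and margin: 17.5 − (21.21 − 17.57) = 13.86. Pain power: Φ(13.86/(21.53 × √(2/131)) − 2.2115) = 99.9%, consistent with the stated 99%. QoR power cannot be reproduced because the SAP gives no QoR effect or SD, so QoR is treated below in SD units.

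**Is the branch reachable?** Trigger: 0.05 × 450 = 22.5, so 23 patients. Interim: 4/75 = 5.3%, exact 95% CI 1.5% to 13.1%. Leaving out the patient randomised to intercostal block gives 4/74 = 5.4%. This is one arm and pain only, so it shows the branch is plausible and no more.

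**Illustration for QoR (assumed inputs).** 30% of patients are high-risk and score 1 SD worse. A share *a* of high-risk and *b* of other patients lack the outcome.

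- Missing in an arm: m = 0.3a + 0.7b
- High-risk share among those observed: q = 0.3(1 − a)/(1 − m)
- Unadjusted complete-case bias: q(TEA) − q(PVB/ICNB), in SD
- SE = √(1/(131(1 − m₁)) + 1/(131(1 − m₂)))
- False superiority per comparison: 1 − Φ(2.2115 − bias/SE)

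Case 1: TEA 3% missing, unrelated to risk. Case 2: TEA 5.3% missing (the interim figure), with the same ratio a/b as in the other arms. The share of 450 is 131 × (2m + m(TEA))/450.

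| Case | a/b in PVB and ICNB | m | q (PVB/ICNB) | q (TEA) | Share of 450 missing | Bias (SD) | False superiority | SMD of driver |
|---|---|---|---|---|---|---|---|---|
| 1 | 20%/2% | 7.4% | 0.259 | 0.300 | 5.2% | 0.041 | 2.9% | 0.09 |
| 1 | 25%/5% | 11.0% | 0.253 | 0.300 | 7.3% | 0.047 | 3.3% | 0.11 |
| 1 | 40%/5% | 15.5% | 0.213 | 0.300 | 9.9% | 0.087 | 6.1% | 0.20 |
| 2 | 20%/2% | 7.4% | 0.259 | 0.271 | 5.9% | 0.012 | 1.7% | 0.03 |
| 2 | 25%/5% | 11.0% | 0.253 | 0.279 | 8.0% | 0.026 | 2.2% | 0.06 |
| 2 | 40%/5% | 15.5% | 0.213 | 0.273 | 10.6% | 0.060 | 4.0% | 0.14 |

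With the same pattern in all arms the bias is 0 and false superiority stays at 1.35%. If the high-risk effect is 0.5 SD instead of 1 SD, false superiority is 2.0% to 3.0% in case 1 and 1.5% to 2.4% in case 2.

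**Opposite direction.** 40%/5% in TEA and 3% in PVB/ICNB: 131 × (0.155 + 0.06) = 28.2 missing, 6.3% of 450. The effect with 90% power at 131 per arm is (2.2115 + 1.2816) × √(2/131) = 0.432 SD. With these missing data SE = 0.130. Power is Φ(0.432/0.130 − 2.2115) = 87% without bias and Φ((0.432 − 0.087)/0.130 − 2.2115) = 67% with it. The two milder patterns in TEA give 3.9% and 4.9% missing, below the trigger.

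**Pain.** Bias × 21.53 gives 0.9 to 1.9 points in case 1 and 0.3 to 1.3 in case 2, against the 13.86-point gap.

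**Do the methods behave as claimed?** A simulation on the pain scale used assumed inputs: 131 per arm, true difference 3.64, residual SD 19, and a binary factor with 40% prevalence and a 20-point effect.

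- MCAR, 10% missing: full data 3.67, complete-case 3.68, weighted 3.67.
- The factor drives missingness in one intervention arm only, 5/10/20% missing: full data 3.62/3.67/3.55; unadjusted complete-case 3.21/2.76/1.56; weighted 3.63/3.67/3.56; complete-case adjusted for the factor 3.63/3.63/3.59.

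**The case against.** The strongest reply is that the plan is not left with a bare complete-case analysis. The covariate adjustment still runs at 5% or more, and if missingness depends on recorded baseline factors, complete-case regression on those factors is itself valid under MAR. The simulation confirms this. It stands, and it means the QoR figures above show what happens when the driver is not adjusted for.

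But covariates are chosen by observed imbalance and clinical judgement, not because they predict missingness. The driver's SMD in the illustration is only 0.03 to 0.20. The missing-data section sets no cut-off, so a small SMD does not rule adjustment out; nothing requires it either. The separate regression under Additional analyses needs an SMD above 25%, which none of these cases reaches.

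Other points that stand:

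- Prevalence, effect and missingness patterns are assumptions. Case 2, closer to the interim figure, gives the smaller effects.
- The interim figure says nothing about QoR, and the SAP does not say that those four patients failed its completeness rule. One QoR score from POD 0 to POD 2 counts as complete, which makes 5% harder to reach for QoR.
- The subgroup step is labelled exploratory and bears on generalisability, so it does not change the test.

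One might add that the plan does not forbid imputation under MAR, since it lets the mechanism guide the methods. The section then states which method goes with which mechanism, and that mapping is the error.

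**Conclusion.** The concern holds. The SAP assigns imputation and weighting to the mechanism where they are least needed. Under MAR it plans neither for the co-primary outcomes, and the restriction it adds instead can neither detect nor correct bias. That reading of the text is firm.

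The size is conditional. It requires at least 23 patients lacking the outcome, missingness or its drivers that differ between arms, and a driver that is left unadjusted. Under the assumed patterns, one-sided false QoR superiority is 1.7% to 6.1% against 1.35%, or power drops from 87% to 67% in the one opposite case examined. Pain non-inferiority is not threatened in these cases if the true difference is near the pilot value. Whether the branch will be reached is unknown. This should be fixed, but it does not undermine the design.

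**What to change.** In Patient replacement and missing data:

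1. Whenever 5% or more of outcomes are missing, take MAR as the working assumption. Run multiple imputation by chained equations or inverse probability weighting on both co-primary outcomes, using arm, centre, baseline score, prognostic factors and any observed postoperative scores. Report the result beside the complete-case analysis.
2. For QoR-15, an alternative is the mixed model already planned, with a specified contrast for the mean of POD 1 and 2.
3. Delete the restriction to subgroups closest to the complete-case estimate.
4. Imputation or weighting under MCAR may stay as a supportive analysis. A delta-adjusted sensitivity analysis for data missing not at random is optional.

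The cost is SAP wording and a modest amount of extra analysis, with no new data or patients. The change should be made before the outcome data are analysed, so that the method is not chosen after the results are seen.
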